### 12.5 Dosage and Dosing Schedule

P1101 will be administered SC during the study visits every 2 weeks. Subjects will receive an initial dose of 100 µg at Week 0, 150 µg at Week 2, and then 200 µg at Week 4, etc., i.e. dose escalation by 50 µg biweekly until 500 µg, or until response will be achieved. The dose can be further adjusted to prior dose for safety and tolerability reasons, but should preferably remain fixed for the treatment period.

The study drug should be administered SC into the abdominal skin around but not within 5 cm of the navel. If the abdomen appears inappropriate or unfavorable for injection according to the Investigator's judgment, study drug can be injected SC into the thigh. At the time of dispensing, the person administering the study drug will note the date and time of administration, both of which are then to be documented into the subject's eCRF.

A standardized dosing paradigm will be used to determine dose adjustments for safety and tolerability so that each subject will receive their most appropriate dose (Section 12.5.2).

### **12.5.1 Aspirin**

All subjects should receive low-dose aspirin (75-150 mg/day) as background therapy unless medically contraindicated. In this case, other prophylactic antithrombotic agents may be used. Higher doses of aspirin (>150 mg/day) should not be used except when medically indicated.

### **12.5.2 Dose Reduction and Dose Interruption**

Dose reduction or interruption for P1101 are recommended in subjects experiencing AEs until the AE abates. If intolerance persists after dose reduction or interruption, therapy should be discontinued. These dose changes must be recorded on the Dosage Administration Record and Adverse Event eCRF page.

Dose reduction of the study drugs should be driven exclusively by the safety and tolerability of the drugs under study. If a certain dose is poorly-tolerated and drug-related toxicities arise, the dose has to be reduced to the prior dose, or interrupted, following the scenarios below:

If a subject has a severe (Grade 3 or 4) toxicity, or a drop in absolute neutrophil count (ANC) to below  $0.5 \times 10^9/L$ , temporary interruption has to be implemented until recovery to the condition, which allows treatment continuation (e.g., Grade 1 mild intensity). Treatment re-initiation has to occur from the prior lower dose than those that caused the toxicity. For example, if Grade 3 AE occurs at 500 µg, treatment re-initiation will occur with 450 µg.

If a subject has a Grade 2 toxicity, or a drop in ANC to below  $0.75 \times 10^9/L$  but higher than  $0.5 \times 10^9/L$ , dose decrease without treatment interruption should be considered.

Grade 1 toxicity should not lead to dose reduction or interruption.

Dose re-escalation may be omitted in those subjects who do not recover from previous toxicity.

## **13 COMPLIANCE**

P1101 will be supplied by the Sponsor. The study drug is to be prescribed only by the Principal Investigator or the designee. Under no circumstances will the Principal Investigator allow the study drug to be used in any settings other than those specified and directed by this protocol.

The Principal Investigator or designee is responsible for ensuring that all drug supplies are kept under lock and key, with access limited to the study team. The Investigator or designated study personnel will maintain accountability of all study drugs received, dispensed, and returned. Drug supplies for each subject will be inventoried and accounted for throughout the study. The pharmacist/designated person must maintain accurate records of the receipt of all study drugs shipped by the Sponsor, including date received, lot number, expiration date, amount received, and the disposition of all study drugs. If any damage in the clinical drug supply shipments occurs, the Investigator should contact the Sponsor/designee immediately. The inventory will be made available to the monitor to verify drug accountability during the study.

Compliance with the dosing regimens will be calculated by the Sponsor based on the drug accountability documented by the site staff and monitored by the Sponsor/designee (injection counts).

Drug administration will also be recorded in each subject's eCRF. An accountability log will be kept, indicating disposition of study drug; this log will be kept in the On-Site Study File.

## **14 PRIOR AND CONCOMITANT THERAPY**

All medications (i.e., over-the-counter drugs and blood products) taken within 3 months (12 weeks) prior to the administration of the study drug, as well as, all concurrent therapies will be recorded in the relevant eCRF pages. All prior nondrug therapies, as well as, all surgeries will be recorded in the relevant eCRF pages. Dose, route, unit frequency of administration, indication for administration, and dates of medication will be captured. Any concomitant medications or changes thereof must be recorded at each visit. If the change influences the subjects' eligibility to continue in the trial, the Sponsor must be informed.

#### **14.1 Allowed Concomitant Therapy**

All subjects should receive low-dose aspirin (75-150 mg/day), unless medically contraindicated. In this case, other prophylactic antithrombotic agents may be used.

Paracetamol (acetaminophen), chlorphenamine (chlorpheniramine), and other antihistamines (used as monotherapy or combination preparations) can be used according to local clinical practice, for the prevention and treatment of injection site reactions associated with peg-interferon.

Moreover, paracetamol (e.g., 500 mg by mouth) or an appropriate dose of another NSAID is recommended to be administered 8 to 10 hours, 24 hours, and 48 hours after the first administration of P1101 in order to avoid potential flu-like symptoms. No prophylaxis will be administered until Visit 2 in order to assess the necessity of prophylaxis and to assess the true rate of IFN-induced flu-like symptoms.

Anti-coagulation therapy: subjects who experience thromboembolic events during the study treatment are permitted to receive full-dose anticoagulants and remain on the study drug based on the judgement of the treating Investigator, except for severe thromboembolic events. All details regarding anticoagulant treatment should be collected and recorded in the Concomitant eCRF page. Details regarding discontinuation due to severe thromboembolic events should be reported on the AEs and discontinuation eCRF page. Severe thromboembolic events are defined as Grade 3 and related AEs. On the Discontinuation eCRF page, the reason for discontinuation would be thromboembolic event.

Phlebotomy is performed aiming at a hematocrit < 45%. When the hematocrit value is 45% or higher, phlebotomy is performed. The volume of phlebotomy per procedure should be 200 to 400 mL per one phlebotomy while monitoring the circulatory dynamics such as blood pressure and pulse. In the elderly and patients with cardiovascular disorders, a small volume (100 to 200 mL) should be considered to avoid rapid changes in hemodynamics.

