### **15.1.3 Treatment Period Week 0 to Week 52**

The first dose of study drug will be administered at 0 hours on Day 1.

All assessments, including local laboratory samples, are to be completed prior to the study drug administration at each visit.

Note: If hematology and/or blood chemistry are done within 7 days prior to Visit 1, they do not have to be repeated.

Please refer to the study flowchart and others (Appendix 1, Appendix 2, Appendix 3) for specific assessments at each visit.

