3.2 Study Visits/ Time-Points

Number of week and number of study visit will be included in label of study visits. The labels will be as follows: Screening, Baseline, Week 2 (V2), Week 4 (V3), Week 6 (V4), ..., Week 52 (EOT), Premature discontinuation (for End-of-Study visit of premature discontinued patients), FU (for Safety Follow-Up visit). Unscheduled visit will be labeled as 'UNS' and presented in chronological order (UNSV.c), v is visit no. and c is the times of unscheduled visit between Visit v to Visit v+1. Unscheduled visit is visit recorded as '※' in EDC.

Assessment visits will be labeled as follows: Week 12 (V7), Week 24 (V13), Week 36 (V19), Week 52 (EOT). Time-window is defined as +/- 3 days of a scheduled visit date. Deviation from the time-window will usually not be adjusted, unless specified otherwise.

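### Protocol 14.1 both recommends and rules out flu-like symptom prophylaxis in the first 48 hours after the first dose, and the planned adverse event tables could not separate the two practices

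*Protocol*

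**What the plan says.** Protocol 14.1 (Allowed Concomitant Therapy) has two adjacent sentences on this.

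- The first says that paracetamol or an NSAID "is recommended to be administered 8 to 10 hours, 24 hours, and 48 hours after the first administration of P1101", and gives the purpose as "in order to avoid potential flu-like symptoms".
- The second says "No prophylaxis will be administered until Visit 2 in order to assess the necessity of prophylaxis", and adds a further purpose: "to assess the true rate of IFN-induced flu-like symptoms".

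Earlier in the same section, paracetamol and antihistamines may be used under local practice "for the prevention and treatment of injection site reactions associated with peg-interferon". No Visit 2 limit is attached to that allowance.

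On timing, Protocol 15.1.3 states "The first dose of study drug will be administered at 0 hours on Day 1", and Protocol Appendix 2 equates Visit 1 with Week 0. SAP 3.2 labels the visits in the order "Screening, Baseline, Week 2 (V2), Week 4 (V3), Week 6 (V4" and so on, and adds "Time-window is defined as +/- 3 days of a scheduled visit date".

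Protocol 14 requires the dates and the indication of every concomitant medication, over-the-counter drugs included, to be recorded. SAP 4.3.6.1 tabulates treatment-emergent adverse events by system organ class, preferred term, maximum severity and relationship, with an overview by 3-month period.

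**The concern.** Medication given to avoid flu-like symptoms is prophylaxis by its stated purpose. The two sentences therefore give opposite instructions to the same patients after the same injection. A site that follows the first departs from the second, and the reverse.

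What is at stake is an aim the protocol sets itself: to learn how often interferon causes flu-like symptoms without prophylaxis, and whether prophylaxis is needed. Safety is part of the primary objective (Protocol 6.1), and these events are likely to matter. Protocol 5.3 lists the drug-related events seen in more than 10% of patients in the earlier dose-escalation study, from most to less frequent; pyrexia is first and influenza-like illness third. If sites read the paragraph differently, the early event rate would depend partly on which sentence each site followed, and the planned tables would not show this.

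**Working it through.** The documents give no flu-like rate and no figure for this aim, so there is nothing to reproduce. The check is one of timing, followed by an illustration on assumed rates.

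**1. Do the two instructions overlap?**

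- First dose: 0 h, Visit 1, Week 0 (Protocol 15.1.3 and Appendix 2).
- Recommended prophylaxis: 8 to 10 h, 24 h and 48 h (Protocol 14.1).
- Visit 2: Week 2 (SAP 3.2). Protocol Appendix 3 agrees, since it places Visit 3 at Week 4. Nominal time: 14 × 24 = 336 h.
- Earliest Visit 2 under the SAP's 3-day window: (14 − 3) × 24 = 264 h.

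Since 48 h is less than 264 h, all three recommended times precede Visit 2 even at its earliest. Both sentences cannot be followed.

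**2. How long is the direct conflict?**

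It runs to 48 h of a nominal 336 h: 48/336 = 1/7, or 2 of 14 days. From 48 h to Visit 2 only the prohibition speaks. Doses taken in the first 48 h can still influence the rate counted over the whole interval to Visit 2.

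**3. Can another reading remove the conflict?**

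- *Visit 2 is the first dosing visit.* Excluded by Protocol Appendix 2 and SAP 3.2.
- *The prohibition covers only prophylaxis after 48 h.* The stated purpose of withholding could not then be met, because symptoms after the first dose would already be under prevention.
- *The firmer wording of the second sentence prevails.* The protocol would then recommend what it rules out, and no section states an order of precedence.

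**4. What would mixed practice do to the tabulated rate?**

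Let f be the share of patients given prophylaxis, p₁ the rate with it and p₀ the rate without it. The pooled rate is f·p₁ + (1 − f)·p₀. All rates below are assumptions.

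| p₀ / p₁ | f = 0 | 25% | 50% | 75% | 100% |
|---|---|---|---|---|---|
| 40% / 20% | 40% | 35% | 30% | 25% | 20% |
| 60% / 30% | 60% | 52.5% | 45% | 37.5% | 30% |
| 30% / 25% | 30% | 28.75% | 27.5% | 26.25% | 25% |

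Only the column f = 0 is the rate the paragraph asks for. The shortfall is f·(p₀ − p₁). At f = 50% that is 10, 15 and 2.5 percentage points in the three rows.

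**5. Would the pooled count reveal which practice was followed?**

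With 30 patients, the exact (Clopper–Pearson) 95% interval is 22.7% to 59.4% for 12/30 (40%) and 7.7% to 38.6% for 6/30 (20%). Both contain every value from 22.7% to 38.6%. The pooled count alone would not tell a reader which sentence had been followed.

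**The case against.** The strongest case on the other side accepts the contradiction and disputes its weight.

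- **The data to sort it out are collected.** Dates and indication are recorded for each medication, so prophylaxed patients can be identified afterwards and the rate in the others estimated. This stands. A reader might infer that the flu-like rate becomes uninterpretable, but the documents do not support that. They support the narrower point that the planned tables would not estimate the named rate if use is mixed. The recoverable estimate would rest on a smaller, self-selected group and would be confounded with site practice.
- **Sites may all read it alike.** This stands too. Nothing in the documents shows how sites understood the paragraph, so divergent practice is a possibility and not a finding. Uniform practice would remove the mixture. If every site gave prophylaxis, however, the tables would describe the rate with prophylaxis and not the one named.
- **The conflict is short.** A reader might take the whole first 14 days to carry opposing instructions. They do not: the recommendation ends at 48 h.
- **Nothing formal depends on it.** The flu-like rate is not a named endpoint in either document, and the SAP plans no analysis of it. The first dose is also the lowest in the escalation and one administration in a 52-week study. This stands and limits the weight of the point.

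What survives is that sites hold two operative instructions that cannot both be obeyed, and that the paragraph's own aim depends on which one they choose.

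**Conclusion.** The point holds in a limited form. Protocol 14.1 contradicts itself for the first 48 hours after the first dose, for all 30 planned patients, and no other section of the protocol or SAP resolves it. If practice differs between patients, the planned tables would give a rate that mixes prophylaxed and unprophylaxed patients and does not estimate the true rate the paragraph names.

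The size of the distortion cannot be taken from the documents. In the illustrations it ranges from nothing, when no patient is prophylaxed, to the full difference between the two rates, when all are: 5 to 30 percentage points across the three assumed pairs.

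The conclusion rests on the visit numbering in Protocol Appendices 2 and 3 and SAP 3.2, and on treating medication given to avoid symptoms as prophylaxis. The primary analysis of complete hematologic response (SAP 4.3.5.1) is untouched. This is a correction that should be made, not a threat to the trial's main conclusion.

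**What to change.** 1. **Protocol 14.1.** Reconcile the two sentences into one instruction covering the period from first dose to Visit 2. Which rule applies is the sponsor's clinical decision.
2. **Same section.** State how that instruction relates to the allowance of paracetamol to prevent injection site reactions. Reconciling the two sentences alone would leave this second route to antipyretic use before Visit 2.
3. **SAP 4.3.6.1.** If any antipyretic use can occur before Visit 2, add a descriptive summary of flu-like adverse events between first dose and Visit 2 by actual use, with the preferred terms listed in advance. Use the recorded dates and indication to separate preventive use from treatment of symptoms already present. Otherwise, patients who took paracetamol because they had a fever would be counted as prophylaxed.

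The cost is one protocol clarification and one extra table, with no new data collection. The drawback is that the table is a small, non-randomised comparison within 30 patients and should be labelled as descriptive.

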## 8.1 Disease Progression/Withdrawal Criteria

The reason(s) for a subject discontinuing from the study will be recorded in the electronic case report form (eCRF). A discontinuation occurs when an enrolled subject ceases participation in the study, regardless of the circumstances, prior to completion of the protocol planned schedule. The Investigator must determine the primary reason for discontinuation.

Discontinuation from the study may occur for the following reasons:

- Disease progression;

For this study, disease progression will be defined as:

- Death due to any cause
- Development of secondary MF, as evidenced e.g. by bone marrow biopsy
- Transformation into acute myeloid leukemia or myelodysplastic syndrome, as evidenced by bone marrow biopsy

- Screening failure;
- Withdrawal of patient consent;
- Severe Noncompliance;
- Worsening of the underlying disease in cases when the further participation (with dose adjustment) is not expected to provide sufficient medical care to the patient;
- Study drug-related adverse event (AE) not recovering within the pre-specified period\*;
  - pre-specified period\*: 8 weeks after discontinuation of IMP administration
- Medical condition unrelated to the underlying disease or study treatment (study drug-unrelated AE);
- Lost to follow-up.

The EoT visit will be performed at the time of study discontinuation.

In case of early treatment discontinuation, the subject should be invited to attend the safety follow-up visit (28 days after the EoT visit).

Subjects who discontinue study drug due to a study drug-related AE or abnormal laboratory value must be followed at least once a week for 8 weeks (and subsequently at 2-week intervals) until resolution or stabilization of the event. If a subject has not recovered from any toxicity within 8 weeks of prematurely discontinuing study drug, s/he must be discontinued from the study, but will continue to be followed for toxicity as described above. In this case, data will not be entered into the database but will be documented in the study log, which is stored at the site.

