### 16.2 Abnormal Clinical Laboratory Test Results

All clinically significant abnormal laboratory tests occurring during the study will be repeated at appropriate intervals until they return to baseline or to a level deemed acceptable by the Investigator and the Sponsor's clinical monitor (or his/her designated representative), or until the abnormality is explained by an appropriate diagnosis. Clinically significant abnormal laboratory tests that result in a change in study drug dosage, discontinuation of the drug, or require intervention or diagnostic evaluation to assess the risk to the subject, or are otherwise clinically relevant, should be recorded as AEs in the eCRF. Clinical diagnosis should be provided whenever possible. If no clinical diagnosis is available, the increase/decrease in the laboratory parameter may be recorded as an AE term. When an abnormal laboratory or test result corresponds to a sign/symptom of an already reported AE, it is not necessary to separately record the laboratory/test result as an additional event.

Laboratory abnormalities that do not meet the definition of an AE should not be reported as AEs. A Grade 3 or 4 event (severe), as per CTCAE, does not automatically indicate an SAE unless it meets the definition of serious as defined in the protocol and/or as per Investigator's discretion. A dose modification or medication for the laboratory abnormality may be required by the protocol in [Section 12.5.2](#) and should not contribute to the designation of a laboratory parameter abnormality as an SAE.

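### Section 14.1 defines the thromboembolic events that rule out continued study drug as Grade 3 and related; read literally this omits related Grade 4 events, which may then be restarted on recovery

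*Protocol*

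**What the plan says.** Protocol section 14.1 (Allowed Concomitant Therapy) deals with thromboembolic events during treatment. Patients who have one "are permitted to receive full-dose anticoagulants and remain on the study drug based on the judgement of the treating Investigator, except for severe thromboembolic events". The exception is then defined: "Severe thromboembolic events are defined as Grade 3 and related AEs". The same paragraph says how discontinuation for such an event is entered in the eCRF.

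Section 12.5.2 sets the general toxicity rule. Its trigger is worded "If a subject has a severe (Grade 3 or 4) toxicity". The action is that "temporary interruption has to be implemented until recovery to the condition, which allows treatment continuation", followed by: "Treatment re-initiation has to occur from the prior lower dose than those that caused the toxicity". It also provides: "If intolerance persists after dose reduction or interruption, therapy should be discontinued".

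Section 16.2 uses the term in the same way as 12.5.2: "A Grade 3 or 4 event (severe), as per CTCAE, does not automatically indicate an SAE".

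Section 8.1 adds a time limit: "If a subject has not recovered from any toxicity within 8 weeks of prematurely discontinuing study drug, s/he must be discontinued from the study".

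Section 15.1.4 says how to record a discontinuation for a severe thromboembolic event but gives no grade. The SAP has no definition of its own. Under section 16.1, AEs are graded by CTCAE version 5.0.

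**The concern.** The definition in 14.1 decides who may stay on drug after a thrombosis, so it works as a stopping rule. It names Grade 3 and neither adds *or higher* nor mentions Grade 4. Read as written, the rule is stricter for the lesser grade: a related Grade 3 event takes the patient off P1101, while a related Grade 4 event is left to the investigator and the general toxicity rule.

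What is at stake is re-exposure after a grave thrombotic event. Section 5.1 names thrombosis as a risk of PV, section 7.4 lists thrombotic events among the AESIs, and inclusion criterion 5 accepts a previous major cardiovascular PV-related event as one ground for entry in cytoreduction-naïve patients. The study is multicentre and each investigator takes this decision, so sites should not have to infer that the graver grade is included. No effect on the CHR rate or its analysis is claimed.

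**Working it through.** **Rule trace.** The protocol states no figure on this point, so the main check is to follow two drug-related thromboembolic events, both recovering within 8 weeks, through the rules.

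| Rule | Related Grade 3 | Related Grade 4 |
|---|---|---|
| 14.1, definition of severe | Met; may not remain on drug | Not met on the literal text; investigator judgement |
| 12.5.2, Grade 3 or 4 toxicity | Restart not open, because 14.1 already takes the patient off drug | Mandatory interruption, then restart at the prior lower dose |
| 12.5.2, persisting intolerance | Not needed | Not triggered if the event resolves |
| 8.1, no recovery within 8 weeks | Not needed | Not triggered |
| 15.1.4, recording of discontinuation | Applies | Gives no grade, so does not extend 14.1 |
| SAP | No definition | No definition |

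Nothing in the right-hand column bars restart.

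**Likely intent.** Sections 12.5.2 and 16.2 both write out Grade 3 or 4 when they use the word severe. Section 14.1 departs from that usage. This points to a slip rather than a deliberate narrower rule.

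**How many patients could be affected.** Inputs:

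- Section 5.3 reports four related SAEs in PROUD-PV. Two were on P1101 (one atrial fibrillation, one rheumatoid arthritis) and two were on HU. Related thromboembolic SAEs on P1101: 0.
- The size of the P1101 arm is not given. Assumed range: 95 (patients who entered the extension on P1101, section 5.3) to 127 (half of the 254 randomised).
- Planned sample: 30 (section 17.2).

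With 0 events in *n* patients, the exact one-sided 95% upper bound for the event probability is 1 − 0.05^(1/n).

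- n = 95: 1 − 0.05^(1/95) = 3.10%; × 30 = 0.93 patients.
- n = 127: 1 − 0.05^(1/127) = 2.33%; × 30 = 0.70 patients.

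These are ceilings, not expected counts; the observed number is zero. They cover every related thromboembolic SAE, so they overstate the subset at issue (Grade 4, recovering within 8 weeks). They assume a population similar to PROUD-PV, and that a Grade 4 event is life-threatening and hence an SAE under section 16.6.

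**The case against.** The strongest reply is that this is copy-editing. The intended meaning can be recovered from 12.5.2 and 16.2, and most investigators would treat a life-threatening thrombosis as severe. The literal reading is also selective: it takes *Grade 3* strictly but has to interpret *related*, which 14.1 does not explain.

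The safeguards are real. Interruption is mandatory and lasts until recovery to a condition for which the protocol gives Grade 1 as the example. Section 5.5 commits to stopping treatment where safety requires it. Thrombotic AESIs follow SAE reporting timelines (16.5), and SAEs reach the sponsor within 24 hours (16.7.1). The residual case is a physician restarting at a lower dose after near-full recovery, with the sponsor informed. The fix also leaves untouched Grade 3 or 4 events judged unrelated, and the word *permanently* is not in 14.1.

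Much of this stands. It is probably a slip, the exposure is small, and the relatedness condition is the protocol's own and is not challenged here. But none of the safeguards prohibits the restart. Where a section supplies its own definition, a site may apply it in preference to usage elsewhere. Permanence is a fair reading of 14.1, which withholds permission to remain on drug and treats these events as grounds for discontinuation.

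**Conclusion.** The concern holds. As written, the stopping threshold in 14.1 omits drug-related Grade 4 thromboembolic events, and no other rule in the protocol or SAP bars restart after such an event that recovers within 8 weeks. It should be fixed on patient-safety grounds. The reason is the gravity of a possible re-exposure and the negligible cost of correction, not frequency: the upper bound is 0.9 to 0.7 patients in 30, on the assumed arm size of 95 to 127 and a population like that of PROUD-PV. The conclusion also rests on reading related as drug-related. Confidence in the textual gap is high. That the authors meant to allow restart after Grade 4 is neither claimed nor likely. Sample size and primary analysis method are unaffected.

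**What to change.** Replace the definition in section 14.1 with:

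> Severe thromboembolic events are drug-related thromboembolic AEs of CTCAE Grade 3 or higher; study drug is permanently discontinued for these events.

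Optionally, add a pointer in 12.5.2 saying that thromboembolic events are governed by 14.1. This is for clarity only; its absence is not a separate contradiction.

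The cost is one reworded sentence and, if wanted, one cross-reference. There are no extra visits, procedures or patients. The downside is that a patient with a related Grade 4 event comes off P1101 and, if withdrawn early, counts as a non-responder under SAP section 4.3.4.1. Even at the upper bound above, this would involve fewer than one patient in 30.
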